C3.1. Inclusion Criteria: age  $\geq$  18, current diagnosis of PTSD in the VA medical record and PCL-5 score of 25 or higher, score of  $\geq$  25 on Montreal Cognitive Assessment (MoCA), willing to reduce or cease opioid medications, willing to attend 12-weeks of yoga and complete 3 assessments. *Due to COVID-19 pandemic, inclusion criteria will be temporarily modified to be age 18 or greater, but less than 65 years of age. Persons 65 or over meeting other inclusion and exclusion criteria will be kept on an list for future consideration but will not be enrolled under current guidance (8/31/20) because of high risk and intervention is not linked to clinical care services.*

C3.2. Exclusion Criteria: serious or unstable psychiatric illness (e.g. psychosis, mania), suicidal or homicidal ideation, < 3 months since major trauma event, moderate or severe cognitive impairment, practiced yoga > 2x in the last 6 months, coexisting medical illness with

yoga contraindicated, affirmative response to any questions on the COVID-19 Pre-Visit Screening Tool.

C3.3 PCL-5. The PCL-5 is a 20-item self-report measure assessing 20 DSM-5 symptoms of PTSD.

C3.4. MoCA is a brief screen for cognitive impairment. We will include those with a score of  $\geq$  25, based on the Youdon index [to ensure that participants are able to understand the informed consent document, their rights as a participant, the assessments, and the intervention instructions.]

C3.5. VA comprehensive suicide screen. Participants will be asked about suicidal thoughts, intent, and behavior, as well as assessment of risk and protective factors as outlined in VA guidelines.

C4. Randomization. After the initial assessment, participants are randomized to either enhanced yoga or the R/HE intervention. Randomization will occur via a web portal linked to a secure file containing two blocks of 20 randomized digits to provide balanced randomization. Research staff will not have access to the file.

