C6. The Mantram Repetition Program (MRP) is a portable meditation-based intervention that has been shown to be effective for treating PTSD and other psychological symptoms/disorders. MRP teaches a set of portable tools, including a) repeating a self-selected "mantram": a word or phrase that provides spiritual strength or meaning for that individual; b) slowing down: refers to slowing down thoughts and raising awareness; also setting priorities so one is not rushed; and c) one-pointed attention: refers to concentrating on one thing at a time instead of "multi-tasking", thereby staying in the present moment and conserving energy. These three tools work together to interrupt negative thoughts and emotional states such as anger, irritability and hyper-arousal, and in turn, improve quality of life. The spiritual focus of the mantram is designed to create personal meaning and inspiration by tapping into inner spiritual resources when the phrase is used. However, religiosity is not emphasized, and participants can choose any phrase that inspires them. The MRP has been manualized (Appendix 6), and the condensed MRP will be taught over the course of 12 weeks. Week 1 will include 30 minutes of MR training, followed by 45 minutes of yoga. Week 2-12 will include about 15 minutes of MR training and dialogue, followed by 60 minutes of yoga. Participants are strongly encouraged to practice MR during daily life, and are asked to self-monitor their use of MR.

C7. Summary of safety information. In multiple full-scale trials of cLBP, and in a broader review of yoga trials, including trials of yoga for cNP, very few adverse events (AEs) have been reported. In studies of yoga for PTSD, no AEs were found when clearly reported. MR studies have not found any AEs attributed to the intervention. If the instructor or research staff become concerned that any participant is at risk of harming him/herself or others, a comprehensive suicide assessment will be performed. If a Veteran is deemed high risk, he/she will be escorted to the walk-in mental health clinic for further treatment.

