**One-leg Stance** - Balance was evaluated using the unipedal stance test, aka the single leg stance. Which is a frequent measure of fall-risk in older adults, but is also frequently used in back pain research. It has been validated and has referenced norms across all adult age groups. The test was administered by research staff with calibrated stopwatches. The participant was instructed to alternately stand on one leg for as long as they could with both eyes open for a maximum of 60 seconds. They were then instructed to repeat the test with both eyes closed.

**C11. Data Analytic Methods.** Because our aims focus on acceptability, feasibility, fidelity and AEs in preparation for a larger RCT, tests of statistical significance are not required. Intervention acceptability and the feasibility of conducting a full-scale RCT will be evaluated using recruitment rates, recruitment to enrollment ratio, intervention attendance rates, retention rates at 12-week assessment, participant satisfaction, serious and non-serious AE rates, participant assessment burden, and instructor fidelity. Mean differences from baseline to follow-up scores will be calculated for outcome measures.

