**C11.2. Data Analysis and Feasibility Criteria.** Recruitment rates will be compared to the specified goal of a mean of 4 enrolled participants per month. We expect to need 5 screened eligible participants per month because some fail to follow through and enroll. If rates remain below 50% of the goal, feasibility will not be established for a full-scale RCT. Attendance rates in many mind-body intervention studies range between 50-80%. For this study, attendance of 50% or higher will be required to support further research on either intervention. A retention rate of 80% or higher is considered an adequate retention rate at a post-intervention assessment for an RCT. Thus, we will use a slightly more lenient 75% or higher retention to indicate feasibility to proceed. Participant satisfaction rates of 75% or higher (measured as % of participants checking agree or strongly agree) will be used to indicate acceptability of the interventions, with little or no modifications needed prior to a larger study. AEs will be evaluated in collaboration with the VASD IRB and the DSMC. In general, any more than 1-2 serious AEs attributed to either intervention among the 20 participants assigned to each would give cause for pausing the intervention until obvious solutions and modifications were identified. Mean time to complete the questionnaires is estimated at 40 minutes. Mean time of 80 minutes or more would indicate burden issues and review of the battery and/or compensation level. Instructor fidelity of under 75% will indicate a need for retraining and/or clarifications of the instructor manual. Finally, mean changes on outcome measures will be compared to minimum clinically important differences where established.

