## Section 10 - Human Subjects

**10) Describe the characteristics of the proposed subject population. Include age, gender, ethnicity, and health status as appropriate. Note: Data about people are still considered “human subjects” by the IRB, so even if you do not intend to contact the patients whose charts you will review, you still describe the characteristics related to the subjects whose charts you will review.**

- Provide inclusion and exclusion criteria as appropriate. Provide a statement how non pregnancy is confirmed if pregnancy is an exclusion criteria.
- For multisite studies, provide the total number of subjects from all sites and include description of the local site's role as a coordinating center if applicable.
- Indicate the number of VA participants to be studied.
- Indicate the estimated number of consented subjects that will fail the screening process, if any.

Human Subjects Involvement and Characteristics. The study will recruit 32 patients from the VA San Diego Healthcare System with a diagnosis of PTSD, and a diagnosis of chronic low back pain (cLBP) and/or chronic neck pain (cNP).

Inclusion Criteria: age > 18, PTSD Checklist (PCL-5) score of  $\geq 25$ , score of  $\geq 25$  on Montreal Cognitive Assessment (MoCA), willing to reduce or cease opioid medications, willing to attend 12-weeks of yoga and complete 3 assessments.

Exclusion Criteria: serious or unstable psychiatric illness (e.g. psychosis, mania), suicidal or homicidal ideation WITH active plan and/or intent, < 3 months since major trauma event, moderate or severe cognitive impairment, practiced yoga  $> 2x$  in the last 6 months, coexisting medical illness with yoga contraindicated.

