### Screening Measures

Medical History Interview. All participants will complete a standard interview regarding medical history and functioning. In addition, a chart review of the VA patient record will be conducted to assess medical status.

C3.3. The PCL-5 is a 20-item self-report measure assessing 20 DSM-5 symptoms of PTSD. It has been validated in Veterans.

C3.4. MoCA is a brief screen for cognitive impairment. We will include those with a score of  $\geq 25$ , based on the Youdon index to be inclusive, yet ensure that participants are able to understand the informed consent document, their rights as a participant, the assessments, and the intervention instructions.

C3.5. Columbia Suicide Severity Rating Scale. Participants will be asked about suicidal thoughts, plan, intent, and behavior, as well as assessment of risk and protective factors.

Based on data from a previous study, only about 25% or less failed the screening exam. Thus we expected to screen about 44 patients and that 12 or less will fail screening.

Qualitative Interviews (QI) will be conducted with a subset 12 of the 32 participants recruited using the criteria above. Participants will be invited to participate in the QI if they had challenges attending, asked to withdraw from the study, or if they have low satisfaction with the program. However, we will also interview at least 4 participants who attended well and were satisfied with the interventions and study.

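### The two exclusion lists set different rules on suicidal or homicidal ideation, and the two items numbered C3.5 name different suicide screens

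*Combined protocol and SAP*

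**What the plan says.** Eligibility is set out twice in the combined protocol.

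- **Section 9, C3.2** excludes people with "serious or unstable psychiatric illness (e.g. psychosis, mania), suicidal or homicidal ideation, < 3 months since major trauma event", among other items. Nothing limits the ideation item.
- **Section 10, Exclusion Criteria** repeats most of that list but states the item as "suicidal or homicidal ideation WITH active plan and/or intent".

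The suicide screen also appears twice, both times as item C3.5.

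- **Section 9, C3.5** names the VA comprehensive suicide screen, by reference to VA guidelines: "Participants will be asked about suicidal thoughts, intent, and behavior".
- **Section 10, Screening Measures, C3.5** names the Columbia Suicide Severity Rating Scale: "Participants will be asked about suicidal thoughts, plan, intent, and behavior".

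Both descriptions add risk and protective factors.

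Three other parts of the plan bear on the point. C7 says that if staff become concerned about a participant's risk of harm to self or others, "a comprehensive suicide assessment will be performed". C11 lists "recruitment rates, recruitment to enrollment ratio" among the feasibility measures. C11.2 sets the benchmark: "Recruitment rates will be compared to the specified goal of a mean of 4 enrolled participants per month", with feasibility not established if rates stay below half of that goal.

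**The concern.** Two rules in force together give opposite enrollment decisions for the same person. Staff working from Section 10 could enroll a Veteran whom Section 9 excludes. Staff working from Section 9 could turn away a Veteran whom Section 10 does not exclude on this item. Either decision departs from one part of the approved protocol. Every participant must have PTSD, so this criterion bears directly on participant safety.

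The two names for the screen add to the problem. The Section 10 criterion turns on plan and/or intent, yet only the Section 10 description of the screen mentions plan.

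There is a smaller consequence for the pilot's purpose. The recruitment rate and the recruitment-to-enrollment ratio inform the decision on a full-scale trial, and at present neither is tied to one definition of who is eligible.

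**Working it through.** **1. The two criteria side by side**

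| Finding at screening | Section 9, C3.2 | Section 10 |
|---|---|---|
| No ideation | Not excluded on this item | Not excluded on this item |
| Ideation, no active plan or intent | Excluded | Not excluded on this item |
| Ideation with active plan and/or intent | Excluded | Excluded |

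The lists disagree in the middle row only.

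**2. Does either list govern?** Section 9, C3 says its criteria are applied by chart review, a medical history interview and the screening measures that follow. Section 10, Screening Measures, refers to participants recruited under the criteria above it, which in that position is the Section 10 list. Section 11 enrolls people who meet the entry criteria above by self-report and then checks the record. Neither list is marked as superseded, and no rule of precedence is given.

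**3. The two versions of C3.5**

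| | Section 9 | Section 10 |
|---|---|---|
| Named screen | VA comprehensive suicide screen | Columbia Suicide Severity Rating Scale |
| Thoughts, intent, behavior | Yes | Yes |
| Plan | Not mentioned | Yes |
| Risk and protective factors | Yes | Yes |

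The documents do not say whether one screen includes the other.

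**4. The plan's own screening figure.** Section 10, Screening Measures, puts screen failure at about 25% or less and says: "Thus we expected to screen about 44 patients and that 12 or less will fail screening". For 32 enrolled, 32 / (1 - 0.25) = 42.7, or 43, which agrees with about 44. The 12 failures are 44 - 32, and 12 / 44 = 27.3%, slightly above the stated 25%. The figure reproduces to within rounding and does not affect the contradiction.

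**5. Illustration of size.** The documents give no prevalence of ideation without plan or intent. A range of 5-20% is assumed, taken as independent of other reasons for screen failure.

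- Otherwise eligible: 44 x (1 - 0.25) = 33, or 44 - 12 = 32 with the stated maximum of failures.
- People whose status changes: 33 x 0.05 = 1.65 to 33 x 0.20 = 6.6, so about 2-7 (1.6-6.4 with 32).
- Per month over the 8 months of recruitment in C2: 1.65 / 8 = 0.21 to 6.6 / 8 = 0.83.
- Goal: 32 / 8 = 4 per month. Floor: 0.5 x 4 = 2 per month.
- A rate at goal, less the upper figure: 4 - 0.83 = 3.17 per month, still above 2.

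**6. The inclusion lists.** Neither list includes the back or neck pain diagnosis, and Section 10's list omits the PTSD diagnosis in the VA record that C3.1 requires. C1.2 and the opening sentence of Section 10 state both diagnoses in narrative, so they are unlisted rather than absent. This is minor.

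**The case against.** The strongest reply accepts that the lists differ but holds that the safety gap is narrow. Both lists exclude people with an active plan or intent and people with serious or unstable psychiatric illness. Both sections screen for suicidality. C7 provides for assessment and escort to the walk-in mental health clinic, and Section 9.9 has investigators review adverse events weekly, with a stopping provision. All of that is true. But C7 and Section 9.9 act on people already in the study, and none of these provisions says whether someone in the disputed group may enter.

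The second reply is that the screens may differ only in name. The VA screen could include the Columbia scale, and a one-sentence summary that omits plan proves little, particularly as the Section 9 summary does cover intent. This stands as a limit: the documents show two names and slightly different descriptions, and do not establish two different procedures. It is still a reason to name one instrument.

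The third reply is that the prevalence range has no source, and that the 25% failure rate may already count people failed for ideation, in which case 33 is the wrong base. That is fair, and the figures are an illustration only. The contradiction does not rest on them. The reply is also right that C11.2 sets a threshold for the recruitment rate but none for the recruitment-to-enrollment ratio, so the feasibility argument is secondary.

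Finally, reading C3.2 as covering any ideation is an interpretation of an unqualified item. It is the natural one, and the qualifier in Section 10 would serve no purpose if the two items meant the same.

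**Conclusion.** The concern holds. Sections 9 and 10 state different ideation exclusions, both current, with nothing to rank them, and they give opposite decisions for a Veteran with ideation but no active plan or intent. The two C3.5 items name different screens. This must be fixed because it is a safety criterion for entry; that conclusion rests on the text alone and needs no assumption about prevalence.

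The effect on recruitment is secondary and cannot be calculated from the documents. Under the assumed 5-20%, the independence assumption and a base of about 33, the lists would differ for about 2-7 people, and no feasibility threshold would be crossed by that alone.

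**What to change.** Reconcile C3.2 and C3.5 in Section 9 with the exclusion list and C3.5 in Section 10. The result should be one eligibility list with one ideation criterion and one named screening instrument, used in both sections and on the screening form. Which criterion and which instrument is for the clinical investigators to decide; this review takes no position. Report the recruitment rate and the recruitment-to-enrollment ratio against that list.

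In the same amendment, add the chronic low back and/or neck pain diagnosis to both inclusion lists, and the PTSD diagnosis in the VA record to Section 10's list. Bringing the text to one list also means settling its other differences: the age limit is at least 18 in C3.1 but above 18 in Section 10, and the temporary COVID-19 upper age limit and the COVID-19 screening exclusion appear only in Section 9.

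The cost is a protocol text amendment and an aligned screening form, with no added procedures or participants.

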C1.1. Aim 1 & 2: The interventions will be adapted in four main ways; a) to safely benefit cNP patients; [b) to ensure it is trauma-sensitive; c) includes additional emphasis on relaxation and stress reduction; and d) to include shorter MRP training sessions. Aims 1 and 2 will leverage ongoing work from the PI's current NCCIH-funded R34 in which the yoga for clBP intervention is being adapted to benefit cNP patients. To ensure trauma-sensitivity, study investigators will build on an intervention designed by co-inv. [name] and other study RR&D-funded protocols (Drs. [name] and [name]) to align the intervention with principles outlined by Emerson et al. The additional relaxation and stress reduction emphasis is designed to alleviate PTSD symptoms in addition to chronic pain.] The MRP will be shortened to an initial 30-minute training followed by 15-minute brief interventions sessions and home practice assignments by [name] who has done preliminary work on adapting MRP for briefer sessions and delivery by phone or Internet. Study investigators will review literature, other protocols, and the revised MRP prior to participating in a half-day intervention refinement conference at VASD. Further intervention refinement will occur at project meetings and a manual will be produced.

C1.2. Aim 3: [we will recruit and randomize 32 VA patients formally diagnosed with PTSD and chronic clBP and/or cNP to enhanced yoga or the R/HE control. We plan to recruit starting in month 4, and will begin randomizing when we reach enrollment of 16, which is expected by month 6-7. The first set of interventions will start in month 8 and run for 12 weeks. We will repeat this process with ongoing recruitment of another 16 participants between months 8-12, with interventions running months 13-16. Participants will complete physiological and self-reported outcomes assessments at baseline, 12 weeks, and 18 weeks after enrollment. Assessments will take about 40 minutes each and participants will be compensated \$40 for each completed assessment. We will also conduct qualitative interviews with 7-8 yoga participants and 4-5 R/HE comparison participants to obtain in-depth feedback on satisfaction and areas that could be improved before a larger trial is conducted.] If feasibility, acceptability, and safety are established, the primary health outcome of interest for a subsequent trial is pain-related disability/ functioning (Roland Morris Disability Questionnaire (RMDQ)).

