C2. Recruitment. We will recruit a total of [32 Veterans] over the course of 8 months. Co-I [name] serves as Director of Outpatient Mental Health at the Medical Center and meets regularly with providers and the directors of the other mental health clinics, and will orient them to study goals. [name] is Director of the Behavioral Medicine Service and part of the Mental Health Integration Team. She serves as a liaison between mental health clinics and primary care, and also treats and evaluates chronic pain patients. [name] will alert primary care and mental health providers to study goals and criteria. [name] also has experience recruiting chronic pain patients with the help of [name] in primary care clinics and through [name] of the Pain Management service. VA patients will be directly targeted via flyers posted in common areas of VA facilities. In sum, study investigators have extensive experience recruiting PTSD and chronic pain patients at VASD, where ~ 40,000 Veterans have chronic pain, 10-15,000 have PTSD, and 5-6,000 have both conditions. *In-person recruitment will be limited and conducted following RAMP up guidelines, including social distancing, the use of PPE, COVID-19 consent addendum, and COVID-19 symptom screening.*

C3. Screening and Inclusion/Exclusion Criteria. Recruitment staff will conduct a brief pre-screen by phone and schedule interested patients for a screening visit to obtain informed consent and HIPAA authorization. Inclusion/exclusion criteria will be applied using a chart review of the VA medical record, a standard medical history interview, and the screening measures described below. English literacy is required. Participants are asked to not perform other mind-body therapies during the study. *Due to COVID-19 pandemic, procedures have been developed to conduct the formal study clinical screening remotely whenever possible to limit in-person research activities. In-person screening for subjects at normal risk will be conducted following RAMP up guidelines, including social distancing, the use of PPE, COVID-19 consent addendum, and COVID-19 symptom screening.*

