**C9. COVID-19 and Intervention Locations. Group intervention will not occur in Phase**

**Orange. They will only commence if we are moved to Phase Yellow.** The Yoga + MR intervention is scheduled to be held in the back of the VASD chapel area on Wednesdays afternoons from 2-3:30PM. When chairs are cleared, this area is approximately 40 ft x 50ft or 2000 square feet area. This has been approved by Chaplain [name]. This large area allows for social distancing of 10 feet or greater between participants. With two cohorts, 8 participants are randomized to each intervention at a time. Attendance is expected to be 6-8 subjects each session. The Relaxation class intervention will also be held in the same space. Subjects at normal risk will be allowed to attend following RAMP up guidelines, including social distancing, the use of PPE, COVID-19 consent addendum, and COVID-19 symptom screening.

**C10. Measures.** Measures will include questionnaires and two physiological measures. Questionnaires are described in section 9.8 To reduce in-person contact during the COVID-19 pandemic, we will allow participants to complete follow-up assessments by mail if they cannot be scheduled for an in-person assessment, or if their status changes from normal risk to higher risk, or if they become infected. If this occurs, we will forego the physiological assessments below.

Physiological measures include grip strength and a one-leg balance test.

**Grip Strength.** Grip strength in both hands of each participant will be measured using an adjustable, hydraulic grip strength dynamometer (Jamar Hydraulic Hand Dynamometer, Model No. BK-7498, Fred Sammons, Inc. Burr Ridge, IL). Two trials will be conducted for each hand. In cases of current pain flare-ups or recent procedures to a hand or wrist, the affected area is not tested, and the result of the one good hand is used. The best performance of two trials will be selected for each side, and the average of the left and right hand will be used for analysis. Reproducibility for grip strength assessment has been shown to be high:  $r=0.88-0.92$ . Predictive validity of hand grip strength has been shown previously for both disability and mortality.

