## Section 9.9 Data Safety Monitoring Board or Plan

## 9.9) Provide a Data Safety Monitoring Plan (DSMP) or the details of a Data Safety Monitoring Board; if a written plan is available, attach a copy of the plan to the submission form.

The study is a pilot intervention that will randomize 32 participants with PTSD to either yoga plus Mantram repetition or to a relaxation comparison group. Study investigators will review all adverse events on a weekly basis and report them as appropriate to the IRB according to established requirements. Drs.[name] and [name] have clinical and research expertise with PTSD. If the rate of serious adverse events attributed to either intervention results in an imbalanced SEA rate between the two study arms, or is higher than clinically expected, the study will be stopped to assess safety. If adjustments to the intervention to remedy the problem are not obvious or easily made, the study intervention(s) will be discontinued.

Research activities will cease if any participant or study staff member that had recent study interactions with study staff or other participants tests positive for COVID-19 within 3 weeks of those interactions. All at risk persons will be notified of their risk at that time.

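### Randomization blocks of 20 do not close at a cohort of 16, so 8 per class is not assured; the 20 per arm in C11.2 also conflicts with 32 randomized

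*Combined protocol and SAP*

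**What the plan says.** **Allocation method.** Section 9, C4 randomizes participants after the initial assessment, through a web portal linked to "a secure file containing two blocks of 20 randomized digits to provide balanced randomization". Research staff have no access to the file. C4 gives neither the allocation ratio, the content of a block, nor how the two blocks map to the two cohorts.

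**Cohorts and class size.** In Section 9, C1.2 the team "will begin randomizing when we reach enrollment of 16", and the process is then repeated with another 16. Section 9, C9 (COVID-19 and intervention locations) states: "With two cohorts, 8 participants are randomized to each intervention at a time".

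**Total size.** Section 2a gives 32. Section 9, C2 says "We will recruit a total of [32 Veterans] over the course of 8 months". Section 9.9 says "The study is a pilot intervention that will randomize 32 participants with PTSD". C11.2 sets "the specified goal of a mean of 4 enrolled participants per month". Section 10, Screening Measures, says "Thus we expected to screen about 44 patients and that 12 or less will fail screening".

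**Size per arm in the safety criterion.** C11.2 would pause an intervention for more than one or two attributed serious adverse events "among the 20 participants assigned to each".

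**The concern.** There are two mismatches.

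1. A permuted block is guaranteed to be balanced only when it is complete. A block of 20 is not complete at entry 16, so the method in C4 does not by itself produce the eight per intervention that C9 states as fact. It would do so only if each block were also constrained to be balanced at entry 16, and C4 does not say that.
2. Twenty assigned to each arm means 40 participants. The trial randomizes 32, and C9 implies 16 per arm. Nothing in the protocol reconciles the two.

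At stake are agreement between the stated method and the stated class size, and a correct per-arm number behind a criterion that can pause an intervention. Feasibility of randomization is part of Aim 3, and C1 says a similar design will be proposed for the full trial, so an unclear allocation paragraph may be carried forward.

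The list holding 40 entries for 32 participants is not in itself a fault; spare entries do no harm. The problem is the length of the block.

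**Working it through.** **Size per arm**

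- C9: 2 cohorts × 8 = 16 per arm.
- Section 2a, C1.2 and Section 9.9: 32 / 2 = 16 per arm with equal allocation.
- C11.2 goal over the C2 recruitment period: 4 per month × 8 months = 32.
- Section 10 screening: 44 − 12 = 32.
- C11.2 criterion: 2 × 20 = 40. This does not reproduce from any stated sample size. It matches only the length of the allocation list, 2 × 20 = 40.

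**Split of a cohort of 16 taken from one block of 20**

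Assumption: the block holds 10 entries for each arm. The number k assigned to enhanced yoga among the first 16 entries is hypergeometric:

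P(k) = C(10, k) × C(10, 16 − k) / C(20, 16)

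| k (yoga : R/HE) | Probability |
|---|---|
| 6 : 10 | 0.0433 |
| 7 : 9 | 0.2477 |
| 8 : 8 | 0.4180 |
| 9 : 7 | 0.2477 |
| 10 : 6 | 0.0433 |

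- 8:8 in 41.8%, 9:7 either way in 49.5%, 10:6 either way in 8.7%.
- One class exceeds eight in 1 − 0.4180 = 58.2% of cohorts.

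**Both cohorts, one block per cohort**

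- Both 8:8: 0.4180² = 17.5%.
- At least one cohort 10:6: 1 − (1 − 0.0867)² = 16.6%.
- Arm total, by convolving the two cohorts: 16 in 0.3011; 15 or 17 in 0.2285 each; 14 or 18 in 0.0976 each; 13 or 19 in 0.0215 each; 12 or 20 in 0.0019 each.
- So the trial ends 16:16 in 30.1%. Each arm has 15 to 17 in 75.8% and 14 to 18 in 95.3%. The extreme of 12:20 occurs in 0.4%.

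**Other readings of C4**

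If the 40 entries are used in sequence, cohort 2 takes the last 4 of block 1 and the first 12 of block 2. The final arm total is then 10 plus a hypergeometric count from 12 of 20, and P(16:16) = C(10, 6) × C(10, 6) / C(20, 12) = 0.350. If the digits are independent 1:1 draws, P(8:8) = C(16, 8) / 2^16 = 0.196 and P(16:16) = C(32, 16) / 2^32 = 0.140.

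| Reading | Cohort 1 at 8:8 | Cohort 2 at 8:8 | Both at 8:8 | Trial at 16:16 |
|---|---|---|---|---|
| One 10:10 block per cohort | 41.8% | 41.8% | 17.5% | 30.1% |
| List used in sequence | 41.8% | 27.2% | 14.6% | 35.0% |
| Independent draws | 19.6% | 19.6% | 0.196² = 3.8% | 14.0% |

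Under each of these readings a cohort misses 8:8 more often than it meets it.

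**Serious adverse event criterion**

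The wording in C11.2 can be read as exceeded at the second or at the third event. Against 20 these are 2/20 = 10% and 3/20 = 15%. Against 16 they are 2/16 = 12.5% and 3/16 = 18.8%.

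**After the change**

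With blocks of 4, 8 or 16 restarted for each cohort, a full cohort of 16 is 8:8 and the trial is 16:16 with probability 1.

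**The case against.** The eight per intervention in C9 stands in a paragraph on room spacing, next to an expected attendance of six to eight, and reads as a planning figure rather than an allocation rule. With 10:10 blocks the expected number per class is exactly eight, and nothing shows that a class of nine or ten breaches a limit. The percentages depend on a block content and a cohort mapping that C4 does not give. The serious adverse event criterion is a count, offered as a general guide and applied together with the IRB and the monitoring committee, so the count is the same whether the arm has 16 or 20. Section 9.9 separately provides for a review if serious event rates are imbalanced or higher than expected. Finally, 40 list entries and 20 per arm agree with each other, so there may be a single mismatch in total size rather than two faults.

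Most of this stands as a limit on the consequences. The exact percentages are conditional, no feasibility decision is shown to change, and the two uses of 20 may share an origin that the documents do not explain. None of it removes either mismatch. The stated method does not deliver the stated class size under any of the three readings, and 32 participants cannot supply 20 to each of two arms.

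**Conclusion.** The concern holds on both parts. The printed mismatches are certain: block length 20 against cohort size 16, and 20 per arm against 32 / 2 = 16. Sixteen per arm is derived from the total and from C9; the protocol does not state it in those words.

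The size of the first part depends on what a block contains. Across the readings examined, 8:8 is reached in 19.6% to 41.8% of cohorts and 16:16 in 14.0% to 35.0% of trials. A block also constrained to balance at entry 16 would remove the problem, but C4 does not describe one.

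The practical impact is modest. This is a feasibility pilot without significance tests (C11). Allocation remains random and concealed, and the attendance, retention and satisfaction criteria are percentages. The correction is still worth making, because it is cheap and because one of the numbers sits in a safety criterion.

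**What to change.** **C4.** State a 1:1 ratio and permuted blocks whose length divides 16, restarted for each cohort, with spare entries if wanted. Class membership is open to participants and instructors, so a short known block would let later assignments be predicted. Either keep the block size out of documents that staff see, or allocate each cohort in one step. Possible wording for the second option: *When the 16 participants of a cohort have completed the baseline assessment, the portal allocates all of them in one step, 8 to enhanced yoga and 8 to R/HE, in random order.* This fits C1.2, which already waits for 16 enrolled. It has C(16, 8) = 12,870 equally likely results and leaves no later assignment to predict. Whichever option is used, C4 should also say what happens if a cohort does not have exactly 16.

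**C11.2.** Reconcile the 20 assigned to each arm with the 16 implied by C1.2 and C9. Whether the serious adverse event criterion itself changes is for the sponsor.

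**Cost.** One rewritten sentence in C4, one reconciled number in C11.2, and a regenerated allocation file for any cohort not yet allocated. The documents do not say whether randomization has begun. If it has, apply the change only to a cohort still to be allocated, and report the actual arm sizes.
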